7.5 Days 15 and 29 (Follow-up) or Early Termination

- Perform a limited PE to focus on heart and lungs.
- Review and record concomitant medications (Note: if there have been changes in concomitant medications during the study, determine whether the change is due to an AE).
- Measure and record vital signs (BP, HR, Temp, Resp).
- Collect and record SpO2 by Finger Sensor
- Collect blood samples for:
 - o Antibodies to SARS-CoV-2.
 - o Hematology and clinical chemistry laboratory analyses
- Assess and record clinical status according to the following study-specific 6-point scale:
 - 1. Not hospitalized
 - 2. Hospitalized, not requiring supplemental oxygen
 - 3. Hospitalized, requiring supplemental oxygen
 - 4. Hospitalized, on non-invasive ventilation or high flow oxygen devices
 - 5. Hospitalized, on invasive mechanical ventilation or ECMO
 - 6. Death
- Assess and record NEWS2
- Collect nasopharyngeal and oropharyngeal swabs for virologic testing.
- Collect and record adverse events (see Section 8.4 for detailed instructions).
- Assess and record ECOG Performance Status and Study-specific Symptom Status (see Appendix A).

Note: Day 15 visit procedures may be conducted on Day 14 if patient is discharged before Day 15.

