## 3.11. Visit Windows

It is expected that all visits should occur according to the protocol schedule. However, analysis visits will be derived based on study day for all by-visit summaries and analyses. Analysis visit designations are detailed in [Table 3-1](#).

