**Table 3-1 Post-Baseline Analysis Visit Designations**

| Analysis Visit | Analysis Visit Range |
|-----------------------|-----------------------------|
| Day 1                 | Day 1                       |
| Day 2                 | Day 2                       |
| Day 3                 | Days 3-5                    |
| Day 8                 | Days 6-9                    |
| Day 11                | Days 10-12                  |
| Day 15                | Days 13-17                  |
| Day 21                | Days 18-24                  |
| Day 29                | Days 25-33                  |
| Day 45                | Days 34-52                  |
| Day 60                | Days 53-70                  |

In the event there are multiple assessments within a given analysis range, the value closest to the target day (understood to be the day identified in the analysis visit) will be chosen. If more than one measurement are the same distance from the target day, the earlier visit will be chosen.

In data listings, the relative day of all dates will be presented.

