#### 4.3.2. Analysis of Secondary Efficacy Endpoints

##### 4.3.2.1. Analysis of Clinical Status via the Study-Specific 6-point Ordinal Scale

The first secondary endpoint of clinical status as measured by the study-specific 6-point ordinal scale at Day 15 will be analyzed by fitting a cumulative odds model, using the most appropriate approach. Clinical status will be modelled as the dependent variable (ordered from 1 to 6, as defined in [Section 1.2.6.1](#)), and treatment group and disease severity as independent variables; other factors may be added for exploratory purposes. Subjects with missing Day 15 data will have their clinical status imputed in the following manner:

- 1) If patients were discharged prior to Day 15, then their clinical status will be imputed to 'Not Hospitalized' at Day 15
- 2) If patients died prior to Day 15, then their clinical status will be imputed to 'Death' at Day 15
- 3) If there is no evidence of hospital discharge or death, clinical status at Day 15 will be imputed using the multiple imputation method described in [Section 3.10.1](#)

The odds ratios and their 90% CI will be provided. As described in [Section 3.2](#), a test at the two-sided alpha level of 0.10 will be performed for descriptive purposes.

Longitudinal analysis of the 6-point scale over time at each visit will be performed in a similar manner. Clinical status will be modelled as the dependent variable and treatment group, disease severity, visit, and the visit/treatment group interaction term as independent variables. The overall treatment odds ratio and their 90% CI will be provided, along with by-visit odds ratios and 90% CI.

Analyses using the study-specific 6-point scale will be done using the ITT population.

The analysis will also be repeated by the dexamethasone usage subgroup, where patients will be categorized as having received dexamethasone if they received it at any time prior the Day 15 analysis visit assessment.

Stacked bar charts over time will be generated to graphically display the proportion of patients in each level of the 6-point scale by treatment group for the ITT population.

By-subject data listings will be provided.

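### Known discharge or death sets Day 15 clinical status only when Day 15 data are missing, so a windowed inpatient score from Day 13 or 14 can override it

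*SAP*

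**What the plan says.** SAP 4.3.2.1 opens its handling rules with a condition: "Subjects with missing Day 15 data will have their clinical status imputed in the following manner". Under that condition stand three items:

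- Discharge: "If patients were discharged prior to Day 15, then their clinical status will be imputed to 'Not Hospitalized' at Day 15".
- Death: "If patients died prior to Day 15, then their clinical status will be imputed to 'Death' at Day 15".
- Neither known: multiple imputation.

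Whether Day 15 is missing depends on SAP 3.11, under which "analysis visits will be derived based on study day for all by-visit summaries and analyses". Table 3-1 gives the window ("Day 15 | Days 13-17"). Within it the score closest to the target day is used, and "If more than one measurement are the same distance from the target day, the earlier visit will be chosen". SAP 4.3.2.1 itself refers to the Day 15 analysis visit when it defines the dexamethasone subgroup.

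Protocol 7.1 and footnote 3 of the Schedule of Assessments have the scale scored every day in hospital and afterwards only at return visits. Protocol 7.3 lists a Day 14 score. The Day 15 visit may fall from one day early to two days late, and Protocol 7.5 adds: "Note: Day 15 visit procedures may be conducted on Day 14 if patient is discharged before Day 15".

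**The concern.** The discharge and death rules sit behind a condition that the window often prevents from being met. An inpatient score on Day 13 or 14 counts as Day 15 data, so the rules are not reached even when the discharge or death date is on file. The categories that can be wrong are the two ends of the scale, home and dead.

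This is the first secondary endpoint. Secondary objective 2 (Protocol 4.2) asks whether it could be the primary outcome of a later double-blind study, so its odds ratio is meant to inform planning. Protocol 9.6 expects some discharges before Day 15 and reports difficulty with return visits. A subject with no score after discharge is therefore a foreseeable pattern.

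**Working it through.** The plan gives no figure for this endpoint to reproduce. The total of about 50 (25 per arm) comes from the primary log-rank calculation and serves here only as a denominator.

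**1. The selection rule.** Among scores on days d = 13 to 17, choose the smallest |d − 15|; on ties choose the smaller d.

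**2. Subjects discharged before Day 15.**

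| Last inpatient score | Next outpatient score | Distances from Day 15 | Score used |
|---|---|---|---|
| Day 12 or earlier | none by Day 17 | window empty | missing, so category 1 (correct) |
| Day 13 | Day 14, 15 or 16 | 2 v 1, 0 or 1 | outpatient (correct) |
| Day 13 | none by Day 17 | 2 | inpatient |
| Day 13 | Day 17 | 2 v 2, tie | inpatient |
| Day 14 | Day 15 | 1 v 0 | outpatient (correct) |
| Day 14 | none by Day 17 | 1 | inpatient |
| Day 14 | Day 16 | 1 v 1, tie | inpatient |
| Day 14 | Day 17 | 1 v 2 | inpatient |

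Return visits on Days 16 and 17 are within the permitted visit window. I enumerated discharge on Day 13 or 14, last inpatient score on that day or the day before, and next outpatient score never or on Days 14 to 18. This gives 23 patterns, of which 10 select an inpatient score: 6 because no return score falls in the window, 3 through the tie rule, and 1 because Day 14 is closer than Day 17. These are patterns, not probabilities. Discharge on Day 11 or 12 gave none.

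**3. Deaths.** For death on Day 13, 14 or 15 with no category 6 entered, an alive score from Day 13, 14 or 15 can be selected. If category 6 is entered on the death date and no alive score stands on that date, death is selected correctly. Death on Day 15 itself falls outside the SAP's rule, which covers only earlier deaths. Separately, a subject discharged and then dead before Day 15, with no score in the window, meets both the discharge and the death item. No precedence is stated.

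**4. How many.** The documents give no discharge rate. Assumption: exponential time to discharge with median m and L = ln 2 / m. Then P(discharge on Day 13 or 14) = exp(−12L) − exp(−14L).

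| m (days) | P | Of 50 |
|---|---|---|
| 5 | 0.046 | 2.3 |
| 7 | 0.055 | 2.7 |
| 10 | 0.056 | 2.8 |
| 14 | 0.052 | 2.6 |

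The curve peaks near m = 9: 0.3969 − 0.3402 = 0.0567, or 2.8 of 50. Under this assumption these counts are ceilings on mis-scored discharges, because subjects with a closer outpatient score are classified correctly.

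**5. Difference between arms.** Across these medians the expected number per arm runs from 25 × 0.046 = 1.15 to 25 × 0.0567 = 1.42, a gap of under 0.3 subject. As an illustration, assume 80% v 65% at home on Day 15: OR = (0.80/0.20)/(0.65/0.35) = 2.15. Mis-scoring 5% of subjects in both arms gives (0.75/0.25)/(0.60/0.40) = 2.00. This is a home/not-home odds ratio, not the cumulative odds ratio that the SAP will fit.

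**6. Other planned analyses.** The last-observation-carried-forward sensitivity analysis (SAP 4.3.2.1.1) replaces only the multiple imputation step. The dichotomized analysis drops subjects after discharge or death. Neither corrects the derivation. The longitudinal model inherits it: the Day 8 window is Days 6 to 9, so after discharge on Day 7 an inpatient Day 7 score ties with a Day 9 outpatient score (|7 − 8| = |9 − 8| = 1) and wins.

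**The case against.** Few subjects can be affected, and only under conditions. The documents do not say how the discharge day is scored; if category 1 is entered on leaving on Day 14, that score beats any Day 13 score and is right. Protocol 7.5 permits the Day 15 procedures on Day 14 but does not require an inpatient category to be recorded. Deaths are serious adverse events with a recorded date, so a missing category 6 may be rare. The p-value is descriptive (SAP 3.2). Discharge and death also enter other analyses that do not use this derivation: time to clinical recovery, duration of hospitalization and all-cause mortality. All of this stands and limits the size of the point.

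One could also read missing as having no score on calendar Day 15, which would remove the main problem. The SAP does not say so, and SAP 3.11 points the other way.

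Two stronger readings are tempting. First, a reader might infer bias between arms, because treatment may change discharge timing. Placing all of a 5% error in one arm of the illustration moves 2.15 to (0.75/0.25)/(0.65/0.35) = 1.62 or to (0.80/0.20)/(0.60/0.40) = 2.67. But the probability of leaving on Day 13 or 14 is nearly flat across plausible medians, and nothing in the documents supports one-sided error. Second, a reader might infer that a subject readmitted before Day 15 is set to not hospitalized. The discharge rule needs missing data, and a readmitted inpatient is scored daily, so it would not normally apply.

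**Conclusion.** The point holds as a derivation defect of minor to moderate weight. Read literally, the SAP can assign an inpatient category to a subject known to be home, or an alive category to a subject known to be dead, and no text gives the known status precedence. For discharges this requires departure on Day 13 or 14, an inpatient category as the last score, and no outpatient score closer to Day 15. For deaths it requires that no category 6 was recorded.

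The number affected cannot be derived from the documents. Under the exponential assumption, the ceiling for discharges is about 2 to 3 of 50. The expected consequence is modest misclassification at the extremes of one descriptive secondary endpoint. No difference between arms has been shown, and the primary endpoint is untouched.

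**What to change.** In SAP 4.3.2.1, derive Day 15 status for all subjects in this order, before any windowing:

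1. Category 6 if death is known to have occurred by Day 15.
2. Otherwise category 1 if the subject is known to be discharged and there is no record of being back in hospital on Day 15.
3. Otherwise the windowed score under Table 3-1.
4. Multiple imputation only if status is still unknown.

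Apply the same order at each visit of the longitudinal ordinal model. This also settles the overlap between the discharge and death items and brings in deaths on Day 15, a small definitional choice that the SAP should state openly.

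The cost is SAP wording and derivation code. Date of death and period of hospitalization are already listed as collected (SAP 1.2.6.1). Readmission dates are not listed separately, so step 2 relies on whatever record of a return to hospital exists. Because the trial is open label, the order should be fixed before the analysis is run.

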#### 4.3.2.1.1. Sensitivity Analysis

The following sensitivity analyses are planned for supportive inference using the ITT population:

- 1) The status of clinical recovery at Day 15 analysis will be repeated using the single imputation method of Last Observation Carried Forward (LOCF) rather than the multiple imputation approach described in [Section 3.10.1](#)
- 2) Clinical status will be dichotomized over time, where subjects will be classified as either improved (Yes) or declined/no change (No) based on the 6-point scale result from the baseline visit. Subjects who are discharged or deceased over time will not contribute to subsequent timepoints. The treatment effect will be analyzed via generalized linear mixed models using SAS PROC GLIMMIX, with improvement in clinical status (yes/no) as the dependent variable, and treatment group, disease severity, and visit as independent variables. Least-squares means of the treatment group effect on the logit scale (difference on the log odds) will be utilized for analysis, where the odds ratio and corresponding 90% CI will be provided

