##### 4.3.2.3.1. Respiratory Progression

The frequency of respiratory progression as assessed up to Day 29 will be tabulated by treatment group. Respiratory progression is defined as:

SpO2  $\leq 94\%$  on room air or PaO2/FiO2 < 300 mmHg, and

- a. Requirement for supplemental oxygen, or
- b. More advanced ventilator support

The treatment effect will be analyzed via generalized linear mixed models using SAS PROC GLIMMIX, with respiratory progression (Yes/No) as the dependent variable, and treatment group, disease severity, age (in years), and visit as independent variables. Least-squares means of the treatment group effect on the logit scale (difference on the log odds) will be presented, along with a 90% CI and a descriptive p-value from a two-sided alpha-level test.

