#### 4.3.2.5. Reduction in Oxygen/Ventilation Requirements

The frequency of requirement for any supplemental oxygen or ventilation (non-invasive, mechanical, or ECMO), as assessed daily up to 29 days and on Day 45 and 60, if possible, will be analyzed in a similar fashion as respiratory progression in [Section 4.3.2.3.1](#).

In addition, the frequency of requirement for any ventilation requirement (non-invasive, mechanical or ECMO) and either mechanical ventilation or ECMO will be analyzed in the same manner as above.

The analyses on oxygen/ventilation requirements will be performed using the ITT population.

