#### 4.3.2.9. Change in SARS-CoV-2 Viral Load

The change in SARS-CoV-2 viral load in upper respiratory tract specimen as assessed by area under viral load curve (quantitative PCR) as assessed up to 29 days. The area under the curve (AUC) over time for a given subject will be calculated, using the linear trapezoidal rule, as the sum of the maximum viral load for each day up through Day 29. Lower Limit of Quantification (LLOQ) result is considered as negative. An analysis of treatment group differences will be performed on the change in viral load using ANOVA model, with treatment group and disease severity as fixed factors.

The change in SARS-CoV-2 viral load will be analyzed by comparing the change between treatment groups using a mixed model with repeated measures (MMRM). This analysis will assess whether or not there is a difference in estimated change from baseline values between active treatment and SOC by visit using least squares means estimates from the MMRM. SAS PROC MIXED will be used to fit an MMRM with change from baseline in SARS-CoV-2 viral load as the response variable and the following covariates and fixed effects:

- Baseline SARS-CoV-2 viral load (covariate)
- Treatment group (fixed effect)
- Visit (fixed effect, time will be defined in terms of Visits)
- Time by Treatment Interaction (Time\*Treatment)

The covariance structure for the repeated measures in this model will be unstructured (UN). If UN does not converge for the model, a first-order autoregressive (AR(1)) covariance structure will be used.

Changes in viral load will be analyzed using the mITT population.

By-subject data listings will also be provided.

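### The longitudinal 6-point model names no subject effect or clustered variance, so as written its overall odds ratio would get a 90% CI that is too narrow

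*SAP*

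**What the plan says.** SAP 4.3.2.1 first sets out a cumulative odds model for status at Day 15, with one record per subject and with treatment and severity as terms. It then extends this: "Longitudinal analysis of the 6-point scale over time at each visit will be performed in a similar manner". The terms follow: "Clinical status will be modelled as the dependent variable and treatment group, disease severity, visit, and the visit/treatment group interaction term as independent variables". The promised output is: "The overall treatment odds ratio and their 90% CI will be provided, along with by-visit odds ratios and 90% CI". This model is not called mixed, and no subject term, covariance structure or robust variance is mentioned.

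Three other sections also put several visits per subject into one model:

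- SAP 4.3.2.1.1 (improved or not) uses a generalized linear mixed model in PROC GLIMMIX, "with improvement in clinical status (yes/no) as the dependent variable, and treatment group, disease severity, and visit as independent variables".
- SAP 4.3.2.3.1 uses the same model class, "with respiratory progression (Yes/No) as the dependent variable, and treatment group, disease severity, age (in years), and visit as independent variables".
- SAP 4.3.2.5 says that the oxygen and ventilation requirements "will be analyzed in a similar fashion as respiratory progression in" Section 4.3.2.3.1.

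None of the three states a random effect or covariance structure. By contrast, the viral-load repeated-measures model in SAP 4.3.2.9 names an unstructured covariance with a first-order autoregressive fallback.

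**The concern.** A subject's status on this scale at one visit says a good deal about the next: death is permanent, and ventilation or discharge tends to persist. A model with only the listed terms treats 50 subjects seen at 7 visits as 50 × 7 = 350 independent records. The by-visit odds ratios suffer little, because each rests on about one record per subject. The overall odds ratio pools all visits, and its standard error shrinks as if every visit brought a new subject.

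The trial exists to inform a Phase 3 study, and Protocol 9.1 uses significance testing to weigh the strength of evidence across endpoints. An overall odds ratio with a nominal 90% interval that covers much less than 90% would make the longitudinal result look firmer than it is.

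**Working it through.** **The plan's own figure.** The documents give no precision or power figure for these models. The only computed design figure is the sample size for the primary log-rank test (SAP 3.1): medians of 4 and 11 days, 15 days of observation, two-sided alpha 0.10, 90% power, 25 per arm.

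- Event probabilities with exponential times: 1 − 2^(−15/4) = 0.926 and 1 − 2^(−15/11) = 0.611, mean 0.769.
- Freedman's formula with hazard ratio 11/4 = 2.75: (1.645 + 1.282)² × (3.75/1.75)² = 39.3 events. 39.3/0.769 = 51.2, so 52 subjects against the stated 50.

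The figure reproduces closely but has no bearing on the repeated-visit models.

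**Inputs for the check.**

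- Subjects: 25 per arm (SAP 1.2.2 and 3.1).
- Visits per subject, m: SAP Table 3-1 gives 7 analysis visits after Day 1 up to Day 29 (Days 2, 3, 8, 11, 15, 21, 29), and 9 up to Day 60.
- Within-subject correlation, ρ: not in the documents. It is an assumption, shown over a range.

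**Analytic approximation.** For a between-subject contrast averaged over m equally correlated visits, the true variance exceeds the independence variance by the design effect D = 1 + (m − 1)ρ. The interval then has 1/√D of its proper width, and a nominal 90% interval covers 2Φ(1.645/√D) − 1. For m = 7 and ρ = 0.5, D = 1 + 6 × 0.5 = 4, the width ratio is 0.50, and coverage is 2Φ(0.82) − 1 = 59%.

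| m | ρ | D | Width ratio | Coverage |
|---|---|---|---|---|
| 7 | 0.1 | 1.6 | 0.79 | 81% |
| 7 | 0.3 | 2.8 | 0.60 | 67% |
| 7 | 0.5 | 4.0 | 0.50 | 59% |
| 7 | 0.7 | 5.2 | 0.44 | 53% |
| 9 | 0.5 | 5.0 | 0.45 | 54% |
| 4 | 0.5 | 2.5 | 0.63 | 70% |
| 4 | 0.1 | 1.3 | 0.88 | 85% |

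**Simulation of the ordinal model.** A cumulative-logit model with visit × treatment was fitted as if visits were independent, with no true treatment effect, 25 per arm and 7 visits (150 to 250 simulated trials per setting).

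| Correlation | Model SE / true SE, overall | Coverage, overall OR | Coverage, last-visit OR |
|---|---|---|---|
| 0 | 1.04 | 90% | 90% |
| 0.3 | 0.62 | 70% | 90% |
| 0.5 | 0.48 | 54% | 90% |
| 0.7 | 0.50 | 60% | 93% |
| AR(1) 0.8 | 0.50 | 60% | 86% |

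The simulation error of a coverage figure is about √(0.6 × 0.4/150) = 4 percentage points, so the 54% and 60% entries should not be ranked.

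**Yes/no models, only if run with no subject term.** An independence logistic model with treatment, severity and visit (1,500 simulated trials per setting) covered 75%, 63% and 62% at ρ = 0.3, 0.5 and 0.7 with 7 visits. With follow-up cut to a mean of 4 visits, it covered 79%, 72% and 66%. The second set is the closer guide for SAP 4.3.2.1.1, where subjects drop out of the model after discharge or death.

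**The case against.** The strongest reply is that the SAP nowhere says that repeated visits are independent. A list of independent variables is a list of fixed effects, so a subject random effect need not appear in it. The Day 15 text also leaves the fitting approach open, and that latitude may be meant to carry over.

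For the GLIMMIX analyses this reply stands. A reader might infer that all four sets of analyses assume independence, but three are expressly mixed models, which implies a random or covariance term. The fault there is that the term is not named. The extra detail in SAP 4.3.2.9 does not prove that the other sections mean no correlation.

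For the longitudinal ordinal model it does not remove the gap. That model is not called mixed, it is patterned on a single-visit model where clustering cannot arise, and none of its stated terms accounts for repeated visits.

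A reader might also infer that every 90% CI from this model is far too narrow. The by-visit intervals are not: last-visit coverage was 86% to 93%. Nor do the documents fix the size for the overall effect, since they give no correlation, and at ρ = 0.1 with 4 visits the width ratio is 0.88. Daily in-hospital scoring might suggest many more records per subject, but SAP 3.11 keeps one value per analysis window for by-visit analyses.

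Finally, these are secondary or supportive analyses, and SAP 3.2 makes every p-value outside the primary endpoint descriptive. That limits the consequence, but an interval labelled 90% should still cover about 90%.

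**Conclusion.** The concern holds for the overall treatment odds ratio from the longitudinal 6-point analysis. Fitted with the terms given, its 90% CI has roughly 0.45 to 0.6 of its proper width and covers about 54% to 70%. This rests on 7 visits, 25 per arm and an assumed correlation of 0.3 to 0.7. At low correlation or with few visits the shortfall is smaller. By-visit odds ratios are essentially unaffected.

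For the improvement, respiratory progression and oxygen or ventilation models, the finding is an unstated random or covariance structure. The same error would follow only if GLIMMIX were run with the listed fixed effects and no RANDOM term.

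A reader might take this as a threat to the trial's main conclusions. The documents do not support that. The primary log-rank test uses one time per subject. The Day 15 ordinal model, which serves the objective of judging the scale as a future primary endpoint, uses one record per subject.

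**What to change.** In SAP 4.3.2.1, state how within-subject correlation enters the longitudinal ordinal model: either a subject random intercept, or GEE clustered on subject with small-sample-corrected robust standard errors. Choose one before the analysis and state a fallback for non-convergence, a real possibility with 50 subjects and states that seldom change. The choice should be deliberate, because the two estimate different odds ratios. GEE gives a population-averaged one, the same kind as the Day 15 model; a random intercept gives a subject-specific one. If the fallback switches between them, the report should say so.

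In SAP 4.3.2.1.1 and 4.3.2.3.1, name the same subject-level term and its fallback. SAP 4.3.2.5 then inherits it by reference.

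The cost is about a sentence per section and little extra programming, with no new data. The downside is wider intervals for the overall effects.
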